#### **4.1.5      *Palatability Endpoints***

- Total number and percent of patients for each response of palatability:
  - Able to swallow capsule (including food media responses if used).
  - Palatability rating (using a 5-point facial hedonic scale).
  - Parent/guardian interpretation of child's reaction/facial expression (using a 3-point scale).
  - Parent/guardian experience problems in giving medication to child because they refuse to take or throw up immediately after taking.
  - Parent/guardian experience problems in giving dietary supplement to child because they refuse to take or throw up immediately after taking.

#### **4.1.6      *Pharmacokinetic Endpoint***

- The PK data from this study will be incorporated into an existing population PK model in adult HoFH patients.

### **4.2           *Overall Study Design***

This is a single-arm, open-label, multi-centre phase III study to evaluate the efficacy and long-term safety of lomitapide in paediatric patients with HoFH receiving stable LLT (including LA, when applicable). Each patient will participate for up to 120 weeks (about 2.5 years) in the study (see Figure 3).

#### 4.2.1 Study

The study will consist of 5 periods (see Figure 3):

[figure not shown]
1. Screening Period (starting at Week -12, i.e.,  $\leq 12$  weeks prior to Baseline for up to 6 weeks).
2. Stratified Enrolment and Start of Run-in Period (starting at minimum at Week -6, i.e., 6 weeks prior to Baseline for a minimum of 6 weeks):
  - Enrolment will be stratified to ensure approximately equal numbers of patients in the following age groups: 5 to 10 years, 11 to 15 years, and 16 to  $\leq 17$  years (with  $\geq 8$  patients in any individual age group).
  - Patients must be stabilised on current LLT (including LA, when applicable) and established on a diet supplying  $<20\%$  of energy (calories) from fat or  $<30$  g fat, whichever is the lesser amount.
  - Daily supplementation with vitamin E (200 international units [IU] for patients 5 to 8 years of age, 400 IU for patients 9 to  $\leq 17$  years of age) and an EFA supplement containing approximately 200 mg linoleic acid, 210 mg ALA, 110 mg EPA, and 80 mg DHA starting at Week -2.
3. Efficacy Phase (starting at Baseline, i.e., Day [D] 0 for 24 weeks $\pm 3$  days):
  - Approximately 45 paediatric patients with HoFH will be treated with lomitapide given orally, added to their current, stable LLT (including LA, when applicable) established during the Run-in Period.
  - Assuming a withdrawal rate of approximately 33% by Week 24 $\pm 3$  days, this would result in 30 evaluable patients at Week 24 $\pm 3$  days (with  $\geq 8$  patients in any individual age group).
  - After stabilisation of the patient on his/her current MTD of LLT (including LA, when applicable) during the 6-week Run-in Period, treatment with lomitapide will be started as an add-on therapy on D0 of the Efficacy Phase.
  - Dosing will be initiated at the recommended starting dose and escalated to the maximum dose as applicable to the age groups based upon safety and tolerability in addition to LDL-C values (see Section 7.2 *Treatment Schedule* and Table 2).
  - The first dose of study medication will be administered at the study site on D0.
  - During the 24-week Efficacy Phase, patients will be required to remain on the stable LLT regimen (including LA, when applicable) established during the 6-week Run-in Period
4. Safety Phase (starting at Week 24 $\pm 3$  days for 80 $\pm 1$  weeks)
  - Patients will enter the 80-week Safety Phase after the Week 24 $\pm 3$  days assessments have been completed. Each patient will continue receiving the MTD of lomitapide he/she achieved during the Efficacy Phase (unless criteria is met for reducing or increasing the dose) for an additional 80 $\pm 1$  weeks in the Safety Phase.
  - If after Week 24 $\pm 3$  days both the investigator and the sponsor consider a patient 5 to 15 years of age to be eligible for further escalation of the lomitapide dose beyond the maximum recommended dose by the respective age group, the lomitapide dose can be increased to an extent defined by the investigator after consultation with the sponsor based on individual safety, efficacy, and concomitant LLT criteria. If the patient tolerates this new dose for  $\geq 4$  weeks, then this will be considered the new MTD.
  - If after Week 24 $\pm 3$  days, a patient has crossed over into the next age category, the study medication can be escalated to the maximum dose applicable for the new age

category. If the patient tolerates this new dose for  $\geq 4$  weeks, then this will be considered the new MTD.

- During the 80-week Safety Phase, the lomitapide dose can be reduced from the MTD due to tolerability or safety issues, and the patient can be re-challenged after a minimum period of 4 weeks following dose reduction with a higher dose of lomitapide once these issues resolve, but the dose during the Safety Phase cannot exceed the MTD established during the Efficacy Phase unless eligibility for exceptional dose escalation described above is met.
- Adjustments to background LLT (including LA, when applicable) will be allowed at the discretion of the investigator.

5. Follow-up (starting at Week 104 $\pm 1$  week for 4 weeks):

- At Week 104 $\pm 1$  week, eligible patients who complete the study per protocol and are  $<18$  years of age may choose to enter the EAP. Patients  $\geq 18$  years of age may opt to transition to commercial product under the approved product label for adults. For both the patient groups, a follow-up phone call will be conducted at Week 108 $\pm 1$  week to monitor safety including AE and concomitant medication reporting.
- For patients who opt not to participate in or are unsuitable for the EAP, or patients  $\geq 18$  years of age who opt not to transition to commercial product will discontinue lomitapide treatment at Week 104 $\pm 1$  week and enter a 4-week Follow-up period during which they will remain on concomitant LLT (including LA, when applicable). These patients will then attend in person for a Week 108 $\pm 1$  week visit.

**Figure 3 Design of Study**

AE = adverse event; ALA = alpha-linoleic acid; DHA = docosahexaenoic acid; EFA = essential fatty acids; EPA = eicosapentaenoic acid; LA = lipoprotein apheresis; LDL-C = low-density lipoprotein cholesterol; LLT = lipid-lowering therapy; MTD = maximum tolerated dose

1. Stabilise current LLT (including LA, when applicable), establish diet <20% energy from fat or <30 g fat, whichever is the lesser amount, dietary supplementation from Week -2 (daily 200 IU [5 to 8 years of age] 400 IU [ $\geq 9$  years of age] vitamin E and EFA supplement [approx. 200 mg linoleic acid, 210 mg ALA, 110 mg EPA, and 80 mg DHA]).
2. During the 24-week Efficacy Phase, patients will be required to remain on the stable LLT regimen (including LA, when applicable) established during the 6-week Run-in Period.
3. Based on safety, tolerability and efficacy parameters.
4. Adjustments to background LLT (including LA, when applicable) will be allowed at the discretion of the investigator.
5. Dose adjustment rules apply.
6. Eligible patients who complete the study per protocol at Week 104 and are <18 years of age may choose to enter the Expanded Access Programme. Patients  $\geq 18$  years of age may opt to transition to commercial product under the approved product label for adults. For both these patient groups, a follow-up phone call will be conducted at Week  $108 \pm 1$  week to monitor safety including AE and concomitant medication reporting. Patients who opt not to participate in or are unsuitable for the Expanded Access Programme, or patients  $\geq 18$  years of age who opt not to transition to commercial product will discontinue lomitapide treatment at Week  $104 \pm 1$  week and enter a 4-week Follow-up period during which they will remain on concomitant LLT (including LA, when applicable). These patients will attend in person for a Week  $108 \pm 1$  week visit.

#### **4.2.2 End of Study**

The End of Study is defined as completion of the last visit or assessment for the last patient.

#### **4.3 Data Safety Monitoring Board**

An independent DSMB will be assigned to periodically review and evaluate study data for participant safety and to advise for continuation, modification or discontinuation in individual patients and of the study. Interim safety data reviews may be performed by the DSMB at their discretion, at any time, on an 'as needed' basis according to ongoing study results.

The DSMB will have an initial organisational meeting at which time the composition, activities, and responsibilities of the DSMB will be detailed in a Charter as agreed upon by the sponsor and the DSMB members. The DSMB will be comprised of at least 3 members who are not otherwise involved in the conduct of the study, at least 1 of whom will be a statistician. The DSMB will meet at least 3 times during the conduct of the study.

The DSMB in consultation with the sponsor will have the authority to stop the study for any reason including, but not limited to, unacceptable safety risks. If a patient discontinues treatment permanently due to a Hy's law case or comparable signs of liver toxicity irrespective of origin, the DSMB will initiate an immediate recruitment stop as an urgent safety measure and will assess individual benefits and risks for the patients being treated with study medication regarding further therapy.

### **5 STUDY POPULATION**

#### **5.1 Inclusion Criteria**

A patient will be eligible for study participation only if all of the following criteria apply:

1. Male and female patients aged 5 to  $\leq$ 17 years with HoFH as defined by any of the following criteria recommended by the Consensus Panel on Familial Hypercholesterolaemia of the EAS (Cuchel, Bruckert et al. 2014):
  - a. Genetic confirmation of 2 mutant alleles at the LDLR, apo B, PCSK9, or LDLRAP1 gene locus OR
  - b. An untreated LDL-C  $>500$  mg/dL (13 mmol/L) or treated LDL-C  $\geq 300$  mg/dL (8 mmol/L) together with either
    - Cutaneous or tendon xanthoma before age 10 years or
    - Untreated LDL-C levels consistent with heterozygous FH in both parents
2. Baseline LDL-C on LLT ( $C_{max}$  of LDL-C immediately prior to LA, if applicable) of either:
  - a.  $>160$  mg/dL (4.1 mmol/L, no documented CVD) or
  - b.  $>130$  mg/dL (3.4 mmol/L, established CVD defined as aortic valve disease and/or coronary atherosclerosis)
3. Body weight  $\geq 15$  kg or BMI and height both  $>10^{th}$  percentile according to WHO Growth Charts for Boys and Girls 5 to 19 Years of Age (see Appendix 4 *WHO Growth Charts*).
4. Patient and/or his/her legal representative has/have been informed, has/have read and understood the patient information/informed consent form, and has/have given written informed assent/consent.
5. Patient and/or his/her legal representative must be able and willing to follow study procedures and instructions, particularly that:

- a. LLT (including LA when applicable) must be stable for at least 6 weeks prior to Baseline (Run-in Period) and remain stable through Week 24±3 days (end of Efficacy Phase).
- b. The patient must be compliant with both the low-fat diet supplying <20% of energy (calories) from fat or <30 g fat, whichever is the lesser amount starting at the beginning of the Run-in Period and the dietary supplement regimen starting at Week -2 of the Run-in Period, both continuing until completion of the study (and during the EAP/administration of commercial product, when applicable).
6. Postmenarchal female adolescents must be willing to use highly effective methods of birth control that, alone or in combination, result in a low failure rate (i.e., <1% per year) when used consistently and correctly (e.g., implant, injectable, combined oral contraceptive, intrauterine contraceptive device, sexual abstinence, vasectomy or vasectomised partner) during participation in the study (and at least 4 weeks thereafter). Postmenarchal female adolescent patients taking oestrogen-based oral contraceptives should be advised that diarrhoea and/or vomiting may reduce hormone absorption. In case of protracted or severe diarrhoea and/or vomiting lasting more than 2 days, the investigator should advise according to national practice, which additional contraceptive measures (such as sexual abstinence, barrier methods) should be used for 7 days after resolution of symptoms.
7. Patient must be in stable physical and mental health at Screening.

## 5.2 Exclusion Criteria

A patient will not be eligible to participate in this study, if any of the following criteria apply:

1. Other forms of primary hyperlipoproteinaemia and secondary causes of hypercholesterolaemia (e.g., nephrotic syndrome, hypothyroidism).
2. Contraindications for the use of lomitapide according to section 4.3 of the Summary of Product Characteristics (SPC included in the Lojuxta® SPC in lieu of an IB; see Section 18.1 *Source Documents*), such as hypersensitivity to the active substance or to any of the excipients listed in Section 6.1 of the SPC, known significant or chronic inflammatory bowel disease or malabsorption.
3. Moderate (Child-Pugh B, see Appendix 1 *Child-Pugh Score*) or severe hepatic impairment (Child-Pugh C), active liver disease and/or abnormal liver function tests at Screening (AST or ALT >1.5 x ULN and/or total bilirubin >1.5 x ULN in the absence of Gilbert's syndrome or AP >1.5 x ULN [based on appropriate age and gender normal values]).
4. Serum CK >2 x ULN.
5. Chronic renal insufficiency with glomerular filtration rate (GFR) <70 mL/min/1.73 m^2 calculated using the Schwartz formula (see Appendix 2 *Schwartz Formula*).
6. Uncontrolled hypertension (defined as mean systolic and/or diastolic blood pressure ≥95% of normal for age and sex) despite medical therapy.
7. New York Heart Association (NYHA) Class III or IV congestive heart failure.
8. Precocious/delayed puberty or endocrine disorder affecting growth (e.g., hypothyroidism, premature adrenarche).
9. History of drug abuse within the last 3 years or habitual alcohol consumption (defined as >1 ounce [28 g] of liquor or 4-ounce glass [113 g] of wine, or the equivalent, ≥3 times per week).
10. Life expectancy predicted to be <5 years.
11. History of a non-skin malignancy (with the exception of cervical cancer *in situ*) within 3 years prior to enrolment.

12. Treatment with any Investigational Medicinal Product (IMP) within 6 months or 5 times the terminal half-life of the corresponding IMP, whichever is longer, before Screening (Visit 1).
13. Patient is a dependent of the sponsor, of the investigational team or his/her immediate family.
14. Pregnant or nursing women.

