Due to the potential for lomitapide to cause elevations in ALT/AST levels, it should be used in caution in patients who consume alcohol. Further, caution should be exercised when lomitapide is co-administered with agents known to be hepatotoxic (see Section 7.6.3 *Non-Permitted Concomitant Medication, Food or Substances*) and is contraindicated in patients with moderate to severe hepatic impairment and those with active liver disease, including patients with unexplained persistent abnormal liver function tests (see Section 5.2 *Exclusion Criteria*).

In the pivotal phase III study, hepatic fat was measured non-invasively using NMR. Mean hepatic fat content of 20 evaluable patients was 1.0% at Baseline, 8.6% at Week 26, 5.8% at Week 56 and 8.3% at Week 78 (Cuchel, Meagher et al. 2013). In the extension study, 18 patients had  $\geq 1$  assessment of hepatic fat by NMR after Baseline. Median hepatic fat increased from 0.7% at Baseline to 6.5% at Week 78 and was 7.7%, 10.3%, and 10.2% at Weeks 126, 174, and 246, respectively (Blom, Averna et al. 2017).

Clinical data suggest that hepatic fat accumulation is reversible after stopping treatment with lomitapide. For this reason, hepatic fat content will be measured 4 weeks after EoT in patients who opt not to participate in or are unsuitable for the Expanded Access Programme (EAP;

<18 years of age)/opt not to transition to commercial product (≥18 years of age; see Section 8.1.2 *Safety Assessments*).

The most common AEs in the phase III study included abdominal pain or discomfort, nausea, vomiting, dyspepsia, diarrhoea, and constipation. Diarrhoea was the most common symptom. This finding is expected since MTP inhibition is known to cause fat malabsorption and steatorrhoea. As the occurrence and severity of GI AEs associated with the use of lomitapide decreases in the presence of a low-fat diet, patients will start to follow a diet supplying <20% of energy from fat or <30 g fat, whichever is the lesser amount at the Start of the Run-in Period, and will continue this diet until the EoT or through the administration of lomitapide in the EAP (<18 years of age) or during administration of commercial lomitapide (≥18 years of age; see Section 8.6.1 *Diet Instructions and Diet Records*).

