*Reduction and Re-challenge*). For patients on a stable maintenance dose of lomitapide who receive any other weak CYP 3A4 inhibitor, the dose of the medications should be separated by 12 hours (see Section 7.3.3 *Dose Modification for Concomitant Medication*). Use in patients with known significant or chronic bowel disease is also contraindicated since MTP inhibition is known to cause fat malabsorption and steatorrhea. Use in patients with rare hereditary problems of galactose intolerance, the Lapp-lactase deficiency or glucose-galactose malabsorption, are contraindicated in accordance with EU guidance (EC Volume 3B Guidelines, *Medicinal Products for Human Use, Safety, Environment and Information: Excipients in the Label and Package Leaflet of Medicinal Products for Human Use*, July 2003) since the drug product contains lactose (see Section 5.2 *Exclusion Criteria*). Hepatic aminotransferase levels must be determined prior to initiating therapy, and then monitored prior to each dose escalation, and regularly during treatment (see Section 1.2 *Flow Chart of Study and Follow-up*). In the event that hepatic aminotransferases become elevated, a detailed algorithm for dose adjustment or treatment discontinuation is provided (see Section 7.3.2 *Dose Modification, Interruption or Discontinuation for Adverse Events*). This algorithm is based on the approach agreed with the DSMB hepatologist that was used successfully in the pivotal phase III study and is consistent with the FDA's draft guidance *Drug-Induced Liver Injury: Premarketing Clinical Evaluation*, October 2007. Dietary advice, including fat content (see Section 8.6.1 *Diet Instructions and Diet Records*) and supplementation with vitamin E and essential fatty acids (see Section 6.3 *Dietary Supplements*), is also specified, and dosing is escalated gradually to minimise GI side effects and allow for regular hepatic aminotransferase determination (see Section 7.2 *Treatment Schedule*). These elements of safety monitoring are designed to allow the optimum individualised dose to be selected for each patient in order to maximise the benefit of LDL-C reduction, ensure compliance with treatment, and avoid AEs.

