### **9.3 Stratified Enrolment and Start of Run-in Period (Starting at Minimum at Week -6, i.e., 6 Weeks Prior to Baseline for a Minimum of 6 Weeks, Visits 2 to 3**

#### **9.3.1 Visit 2 (Stratified Enrolment and Start of Run-in Period, at Minimum Week -6)**

Upon confirmation of eligibility, patients will come back to the study site for Visit 2 (at minimum Week -6) for stratified enrolment and to start the Run-in Period. At Visit 2, the following procedures will be conducted:

- Dietary counselling (see Section 8.6.1 *Diet Instructions and Diet Records*)
- Dispensing of 2-Day Diet record (used to enable adjustments to the patient's diet before starting study drug; see Section 8.6.1 *Diet Instructions and Diet Records*)
- A urine pregnancy test in all postmenarchal female adolescents (see Section 8.1.2 *Safety Assessments*)
- Record of concomitant medication including LLT and/or LA when applicable (see Section 7.6.1 *Concomitant Lipid-lowering Treatment* and Section 8.1.2 *Safety Assessments*)
- Enquiry about any AEs/SAEs and record in the AE section of the eCRF.

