#### **9.3.2 Visit 3 (Compliance, Week -3 to Week -2)**

The patient will visit the study site for Visit 3 (Week -3 to Week -2) and must present in fasting state. The following procedures will be conducted:

- Dietary counselling (see Section 8.6.1 *Diet Instructions and Diet Records*)
- Dispensing of new and collection of old 2-Day Diet records (see Section 8.6.1 *Diet Instructions and Diet Records*)
- Collection of blood samples for fasting lipid panel (see Section 8.3.1 *Fasting Lipid Panel*)
- Dispensing of dietary supplements (see Section 6.3 *Dietary Supplements*)
- A urine pregnancy test in all postmenarchal female adolescents (see Section 8.1.2 *Safety Assessments*)
- Record of concomitant medication including LLT and/or LA when applicable (see Section 7.6.1 *Concomitant Lipid-lowering Treatment* and Section 8.1.2 *Safety Assessments*)
- Enquiry about any AEs/SAEs and record in the AE section of the eCRF.

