### **9.4 Efficacy Phase (Baseline, D0 to Week 24±3 days), Visits 4 to 10**

#### **9.4.1 Visit 4 (Baseline, D0)**

The patient will visit the study site for the Baseline assessment of the Efficacy Phase at Visit 4 (D0) and must present in fasting state. The following procedures will be conducted:

- Confirmation of patient eligibility using the inclusion criteria (see Section 5.1 *Inclusion Criteria*) and exclusion criteria (see Section 5.2 *Exclusion Criteria*)

- Abbreviated physical examination (including a focused evaluation of general appearance, skin, thorax/lungs, CV, abdomen, and xanthomas) and record of height, weight, BMI, and BSA (see Section 8.1.1 *Eligibility Assessments*)
- Determination of sexual maturation based on Tanner staging (see Section 8.1.1 *Eligibility Assessments* and Appendix 5 *Tanner Staging*)
- Record of 12-lead ECG (read locally, see Section 8.1.2 *Safety Assessments*)
- Collection of information in relation to the most recent standard of care echocardiography on file (if available, see Section 8.1.2 *Safety Assessments*)
- Measurement of vital signs and blood pressure (see Section 8.1.1 *Eligibility Assessments*)
- Pulmonary Function Test (see Section 8.1.2 *Safety Assessments*)
- NMR imaging of liver for hepatic fat assessment; if NMR imaging is contraindicated or not feasible (e.g., due to the need for sedation or general anaesthesia in very young or anxious patients), ultrasound scans will be used at the discretion of the investigator (see Section 8.1.2 *Safety Assessments*)
- Dietary counselling (see Section 8.6.1 *Diet Instructions and Diet Records*)
- Dispensing of new and collection of old 2-Day Diet records (see Section 8.6.1 *Diet Instructions and Diet Records*)
- Carotid intima-media thickness (CIMT, mandatory) and flow-mediated dilation (FMD, whenever possible) using ultrasound scan (see Section 8.4.2 *Assessment of Carotid Intima-Media Thickness and Flow-mediated Dilation*)
- Collection of blood samples for the following tests (see Section 8.1.2 *Safety Assessments*):
  - Complete blood count
  - Comprehensive metabolic panel
  - Liver function tests
  - Fasting lipid panel (see Section 8.3.1 *Fasting Lipid Panel*)
  - Serum level of essential fatty acids
  - Serum lipase
  - Fat-soluble vitamin levels
  - Hormones (TSH, ACTH, serum cortisol [to be measured between 06:00 and 08:00 a.m.], FSH, LH)

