  - In patients who are Tanner Stage  $\geq 2$ , serum oestradiol will be assessed for female patients and serum testosterone will be assessed for male patients
  - Pharmacokinetics (single trough sample, date and time of the patient's last lomitapide dose and time of the sample should be recorded in the eCRF)
- Urinalysis (urine colour, turbidity, pH, glucose, bilirubin, ketones, blood, protein, and white blood cells)
- A urine pregnancy test in all postmenarchal female adolescents (see Section 8.1.2 *Safety Assessments*)
- Dispensing of dietary supplements and collection of used dietary supplement bottles as needed (see Section 6.3 *Dietary Supplements*)
- Dispensing of study medication (see Section 7.2 *Treatment Schedule*): The first dose of study medication will be administered at the study site.

- Palatability assessment: A 5-point facial hedonic scale will be used to record the child's assessment of palatability of study medication on the first occasion that any patient who is unable to swallow the intact capsule(s) and opens the capsule(s) and sprinkles the capsule content on a small amount (1 tablespoon) of either apple sauce or mashed banana (i.e., if a patient tries both food media, assessment will be made at the first instance of taking the study medication with apple sauce and the first instance of taking the study medication with mashed banana). The type of food media (apple sauce or mashed banana) will be captured (see Section 8.5 *Palatability*)
- Record of concomitant medication including LLT and/or LA when applicable (see Section 7.6.1 *Concomitant Lipid-lowering Treatment* and Section 8.1.2 *Safety Assessments*)
- Enquiry about any AEs/SAEs and record in the AE section of the eCRF.

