## 10 COLLECTION, STORAGE AND SHIPMENT OF LABORATORY SAMPLES

The following laboratory tests will be performed at the local hospital laboratories to allow for taking therapeutic decisions upon availability of results:

1. Comprehensive Metabolic Panel: Na, K, Ca, carbon dioxide, Cl, BG, CRP, BUN, creatinine, CK, total protein, and albumin
2. Serum Lipase
3. Liver Function Tests: ALT, AST, GGT, AP, and total bilirubin including direct and indirect bilirubin
4. Fasting Lipid Panel: TC, LDL-C, VLDL-C, calculated Non-HDL-C, TG, apo B, Lp(a), HDL-C, and apo A-I

Please note: Fasting lipid panels will also be analysed in the central laboratory specified in the '*Laboratory Manual*'. As the fasting lipid panel will be analysed at both the local hospital laboratory and the central laboratory, 2 separate samples must be drawn.

5. Complete Blood Count: White blood cell count, haemoglobin, haematocrit, platelet count, red blood cell count, red cell distribution width, MCV, MCH, and MCHC
6. Hormones: TSH, ACTH, serum cortisol, FSH and LH; the blood sample for testing of serum cortisol must be obtained in the early morning (6:00 to 8:00 a.m.)
7. Sex hormones (in patients who are Tanner Stage  $\geq 2$ ): serum oestradiol for female patients and serum testosterone for male patients
8. Urinalysis: urine colour, turbidity, pH, glucose, bilirubin, ketones, blood, protein, and white blood cells
9. Pregnancy Test: Urine pregnancy test strips will be provided to the sites for conducting urine pregnancy tests in female postmenarchal adolescent patients.

The following laboratory tests will be performed at the central laboratories specified in the '*Laboratory Manual*':

1. Genetic Testing: For those patients who have signed a separate ICF for genetic testing, a blood sample will be collected according to central laboratory procedures for genotyping specified in the '*Laboratory Manual*' at Screening (Visit 1) or at a later visit.
2. Fasting Lipid Panel: TC, LDL-C, VLDL-C, calculated Non-HDL-C, TG, apo B, Lp(a), HDL-C, and apo A-I

Please note: As the fasting lipid panel will be analysed at both the local hospital laboratory and the central laboratory, 2 separate samples must be drawn. All samples will be kept for up to 2 years after the study is completed.

3. Fat-Soluble Vitamin Levels: Retinol, alpha tocopherol, 25-hydroxy-D, ratio of alpha tocopherol/total lipids (TC + fasting TG), ratio uncarboxylated osteocalcin/total osteocalcin

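### Exclusion 3 applies its 1.5 x ULN liver limits only at Screening, 6 to 12 weeks before first dose; no rule requires the D0 result to be within them before dosing

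*Protocol*

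**What the plan says.** Protocol 5.2, criterion 3 (same wording in the synopsis), excludes moderate or severe hepatic impairment, and "active liver disease and/or abnormal liver function tests at Screening". It then gives the limits: AST or ALT, total bilirubin (Gilbert's syndrome aside) or AP above 1.5 x ULN.

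The visit schedule then runs as follows:

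- **Visit 2 (9.3.1).** The list opened by "At Visit 2, the following procedures will be conducted" contains no liver function test (LFT).
- **Visit 3 (9.3.2).** The only blood test is "Collection of blood samples for fasting lipid panel".
- **Visit 4, D0 (9.4.1).** The list starts with "Confirmation of patient eligibility using the inclusion criteria" and the exclusion criteria, includes an LFT draw, and adds: "The first dose of study medication will be administered at the study site".

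Other sections bear on the same step. Section 2.6.3 says "Hepatic aminotransferase levels must be determined prior to initiating therapy", and describes the contraindication in active liver disease as "including patients with unexplained persistent abnormal liver function tests". Section 10 has LFTs run at local laboratories "to allow for taking therapeutic decisions upon availability of results". Section 11.3 obliges the investigator to review local results and to grade abnormal ones for clinical significance.

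**The concern.** The sponsor chose a numeric entry limit for a drug whose main known risks include liver toxicity. Section 2.6.3 reports ALT and/or AST above 3 x ULN in 10 of 29 adults in the pivotal study, all managed by dose reduction or interruption. Such a limit protects a child only if it is applied close to first exposure. Here it is applied to a sample taken before the run-in, during which background therapy is stabilised and a low-fat diet and supplements are introduced.

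At D0 a fresh sample exists, but re-confirming criterion 3 as worded points back to the Screening value. A site can follow the protocol exactly and start a child who on that day fails the sponsor's own limit. Once started, a child with ALT 2.5 x ULN is at Level 1 (7.3.2), for which no dose change is prescribed.

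**Working it through.** **1. The plan's own timeline.** The synopsis gives participation of up to 120 weeks. With Screening plus run-in capped at 12 weeks, 12 + 24 (Efficacy) + 80 (Safety) + 4 (Follow-up) = 120, as stated. The 12-week cap is therefore the right upper bound.

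**2. Age of the Screening LFT at first dose.**
- Shortest: no minimum gap before run-in (1.2, footnote A) plus a 6-week minimum run-in: 0 + 6 = 6 weeks = 42 days.
- Longest: Screening at most 12 weeks before Baseline: 12 x 7 = 84 days.

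**3. Which sentence applies the limits to a later sample?**

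| Text | What it requires | What it leaves open |
|---|---|---|
| 5.2, criterion 3 | Limits met at Screening | Any later value |
| 9.4.1 | Eligibility re-check and LFT draw at D0 | Whether the result is known before dosing; which value criterion 3 refers to |
| 2.6.3 | Aminotransferases determined before therapy | Threshold, sample age, bilirubin, AP |
| 10 and 11.3 | Local analysis; mandatory review | Whether review precedes the dose |
| 9.6 | Unscheduled assessments as the investigator sees fit | Any obligation in this situation |

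No row requires a D0 result within 1.5 x ULN before the first dose.

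**4. Values that fail the entry limit but meet no numeric action rule in 7.3.2** (isolated and asymptomatic):
- ALT or AST above 1.5 and up to 2.9 x ULN: Level 1, no modification.
- Total bilirubin above 1.5 and up to 2 x ULN: Level 4 starts above 2, on two occasions.
- AP above 1.5 and up to 5 x ULN: Level 4 starts above 5, on two occasions.

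In addition, a single aminotransferase value from 3 to below 10 x ULN meets no level until confirmed at least 7 days later, because Levels 2 and 3 need two values and only 10 x ULN or more counts at one time point.

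**5. Comparison within the protocol.** Section 8.3.2 requires LDL-C to qualify at Screening and again at Week -3 to -2 before treatment may begin. Exclusion 4 (CK) carries no Screening qualifier, so the D0 re-check reaches it. Only the LFT limits are pinned to the early sample.

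**The case against.** The case on the other side has real weight.

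- **Review is mandatory.** Section 11.3 makes the investigator look at the local D0 result, and 7.3.2 and 7.4 allow dose reduction, discontinuation or withdrawal for an abnormal laboratory finding. This stands, except that none of it is tied to the time before dosing.
- **A site may read 9.4.1 and 2.6.3 together as a pre-dose liver check.** That is reasonable, and many sites would act so. It is still an inference: the Screening sample satisfies 2.6.3, and criterion 3 names Screening.
- **Persistent disease is covered.** The clauses on active liver disease and label contraindications have no time limit and are re-checked at D0. What remains is a new, isolated, asymptomatic rise.
- **The protocol tolerates such values on treatment.** Level 1 children may continue at maximum doses of 20 to 60 mg. An entry limit stricter than the on-treatment action limit is normal, so Level 1 is not itself a fault. The point is only that the chosen entry limit is not applied near first exposure.

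Two stronger readings are tempting. The next scheduled LFT after D0 is Week 4 ±3 days (28 ±3, so D25 to D31), and a reader might infer about four weeks of unwatched exposure. The documents do not support that, because the D0 sample is analysed locally and must be reviewed; the realistic gap is the local turnaround, which is not given. A reader might also take 10 of 29 as a guide to how often the gap would matter. That is an on-treatment rate in adults and says nothing about rises during run-in, for which the protocol gives no frequency.

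**Conclusion.** The gap is real but narrow. The only result that must meet the 1.5 x ULN limits is 42 to 84 days old at first dose, and nothing makes dosing at D0 wait for the fresh result. A child with a new, isolated, asymptomatic rise during run-in can be started against the intent of Exclusion 3.

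The likely harm is small: the starting dose is 2 mg (ages 5 to 15) or 5 mg (16 to 17), the result is reviewed once available, and the investigator can stop. This rests on two assumptions: that local turnaround is short, and that such rises are uncommon. The protocol gives a figure for neither. It would go too far to say that the protocol has no pre-treatment liver safeguard. Minor severity; a cheap improvement.

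**What to change.** 1. In Exclusion 3 (synopsis and 5.2), replace the Screening qualifier by: *at Screening and at Baseline (D0, before the first dose)*.
2. In 9.4.1, state that the first dose is given only after the local D0 LFT result has been reviewed and is within the Exclusion 3 limits. Where same-day results are not available, allow the local sample to be taken a few days before D0, with the maximum number of days named.
3. Allow one repeat LFT before a child is excluded, and state that it is not a re-screening, because 9.2 restricts re-screening to LDL-C, CK and blood pressure. State also how far D0 may move for the repeat when Screening is already close to 12 weeks old.

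Adding an LFT at Visit 3 instead would only shorten the interval to 14 to 21 days and would leave the D0 sample unread before dosing.

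**Cost.** The D0 sample is already drawn, so no new assay is needed as a rule. There is a short wait for the local result, which for children on apheresis has to fit around the lipid draw timed just before the session (7.6.1); early sampling avoids this. Expect an occasional extra or repeat blood sample, and possibly a few run-in failures in a rare disease, which the repeat test should limit.
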